### 3.6 Identification of Source Data

The following source data will be directly recorded on the Case Report Form (CRF):

- Patient demographic data:
  - Age
  - Sex
  - Ethnicity
  - Indication for scar excision
  - Concomitant medications
- Inclusion criteria
- Exclusion criteria
- Physical examination
- Trial medication administration
  - Date of dosing
  - Time of dosing
- Assessment

- POSAS
- VSS
- Adverse events
  - Pain
  - Rash
  - Skin Ulcer
  - Erythema
  - Pruritus
  - Urticaria
  - Erosions
  - Scabbing
  - Infection
  - Depigmentation
  - Hypopigmentation
  - Hyperpigmentation

The following source data will not be directly collected in the Case Report Form (CRF), but will be captured in supportive documentation (EMR):

- Photographs of lesion area
- Ultrasound 3D radiographic images
- Histology report from 5-mm skin biopsy

## 4 Subject Selection Enrollment and Withdrawal

### 4.1 Inclusion Criteria

- Males and females 18 years of age or older.
- Diagnosis of hypertrophic scar by a Mayo Clinic plastic surgeon or dermatologist
- Target disease or condition: Hypertrophic scar
- Subject with a hypertrophic scar that meet all of the following criteria:
  - Linear scar  $\geq 3$  cm to  $\leq 40$  cm in length
  - Present for minimum 6 months
  - Located anywhere in the body except on the face or front of neck
  - Resulting from surgical or traumatic injury, or other scar considered appropriate for surgical excision
- Ability to safely undergo scar excision surgery
- Capacity to provide informed consent
- Ability to comply with protocol
- Subject is judged, by the clinical investigator, to be healthy as evidenced by lack of clinically significant abnormal findings on medical history, physical examination, electrocardiogram, vital signs, and clinical laboratory tests.

### 4.2 Exclusion Criteria

- Subjects identified as having a keloid or a scar not appropriate for surgical excision

- Subjects who are positive for hepatitis B surface antigen (HbsAg), hepatitis C antibody and HIV as determined in screening the subject's electronic medical record.
- Concurrent use of systemic corticosteroids (excludes inhaled or topical steroids), COX-2 inhibitors and/or drugs that are strong inhibitors and inducers of CYP enzymes
- Are immuno-compromised (HIV infected, cancer and other disease affecting the basal immune response)
- Clinically significant cardiovascular, pulmonary, renal, endocrine, hepatic, neurological, psychiatric, immunological, gastrointestinal, hematological, or metabolic disease that is, in the opinion of the investigator, not stabilized or may otherwise impact the results of the study.
- Subjects with renal and hepatic impairment.
- Known allergy or hypersensitivity to the study drug(s) or one of the ingredients of the formulation.
- Any infection or wound in the area to treat including photosensitive dermatosis or inflammatory acne.
- Existence of any surgical, medical or laboratory condition that, in the judgment of the clinical investigator, might interfere with the safety, distribution, metabolism or excretion of the drug
- Participation in another clinical study in the past 30 days or concurrent participation in another clinical trial.
- Patients with poorly controlled diabetes mellitus ( $\text{HbA1c} \geq 8\%$ ), peripheral neuropathy, or known concomitant vascular problems.
- Pregnant or lactating female patients.
- Prisoners.
- Subjects who smoke cigarettes and/or use other tobacco products.

#### 4.3 Subject Recruitment, Enrollment and Screening

Prior to discussing study enrollment with the patient, principal investigator, [name] and/or [name], will discuss with study coordinator to ensure that that target enrollment has not yet been met.. Subjects will be recruited at Mayo Clinic Department of Dermatology and Division of Plastic Surgery in Rochester, Minnesota.

At the time of patient enrollment in the trial the following must be verified:

1. IRB approval of the trial and open enrollment status with both Mayo Clinic and clinicaltrials.gov.
2. Open place on the enrollment log (confirmation from the PI and study coordinator).
3. Patient is willing and able to travel to the Mayo Clinic, Rochester for all tests, treatment and follow up required in the protocol.

At the time of patient enrollment the following will be confirmed and documented:

1. A signed consent form.

2. The existence of a signed authorization for use and disclosure of protected health information.
3. A completed inclusion/exclusion enrollment checklist.

#### **4.4 Early Withdrawal of Subjects**

##### **4.4.1 When and How to Withdraw Subjects**

Subjects may withdraw from the study for any of the following reasons: safety issues, inability or unwillingness to adhere to protocol requirements, or if the subject desires to withdraw from the study. A single subject withdrawn from the study will not be replaced. If two or more patients have withdrawn (with the exception of safety reasons) one of the subjects will be replaced with a new enrollee. The decision to withdraw subjects and the responses below will occur under the following circumstances.

- Patients wishing to withdraw from the study: Patients wishing to withdraw from the study should provide written indication of these wishes.
- Patients unable or uncooperative to continue in the study: If possible, patients should be contacted in an attempt to determine the reasons for the inability to complete the study. After at least three attempts and failure to complete required testing the patient will be considered out of the study.
- Withdrawn from study due to safety reasons: See section below for the response to drug related adverse events and patient withdrawal from the study. Generally, even patients with a drug related adverse event will continue with the test schedule as the test schedule includes minimal risk tests and is used to monitor and gauge continued long term effects of the treatment.

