## 3 Study Design

### 3.1 General Description

This study is a double-blind pilot study of scar excision procedure followed by treatment with either TP in PCCA PP versus PCCA PP silicone base only. Current management for patients with hypertrophic scar includes silicone-based treatment. At our institution we treat patients with scar excision surgery without topical scar cream following the procedure. However, a significant proportion of patients continue to fail this treatment modality leading to scar recurrence. Indeed, individual patient response to therapy varies based on patient characteristics including ethnicity. As such, we plan to treat the same patient with both TP in PCCA PP and PCCA PP alone at different ends of their scar. In this way, we can better determine efficacy of these topical agents in biologically controlled setting with reduced response variability. We plan to enroll patients with minimum hypertrophic scar length  $\geq 3$  cm.

Those patients who successfully qualify based on inclusion and exclusion criteria will be invited to participate in the trial. Following informed consent, eligible subjects will undergo pre-operative tests to include blood work and EKG. Preoperative photographs of the scar site will be taken. Scar quality questionnaires (VSS and POSAS) will be completed and a scar ultrasound performed.. A 5-mm skin punch biopsy will be obtained from the lateral edge of the scar at both the proximal and distal ends of the scars, under local anesthesia. Alternatively, the first punch biopsy may occur prior to the surgical procedure while the patient is under anesthesia. Part of the sample will be stored in formalin and prepared for histological staining. The other portion will be frozen and prepared for molecular analysis. All participants will receive both treatments to be applied either at the proximal end or the distal end of the scar. Treatment application will be randomized. For example, topical agent A will be applied to the proximal end of the scar and will contain either TP

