### 3.2 Number of Subjects

Ten subjects will be enrolled in this trial.

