## 7 Statistical Plan

### 7.1 Sample Size Determination

This is a first in-human exploratory study to determine the efficacy of topical pentamidine. There will be 80% power to detect an effect size of 1.3 standard deviations for the comparison of MED between any two treatment groups. This calculation is based a two-sided unpaired t-test with a type I error of 0.05.

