### 7.3 Subject Population(s) for Analysis

This study will include only subjects who completed ALL study-related procedures and follow up.

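### The completers-only rule in Section 7.3 discards usable scar pairs that Section 4.4.1 does not replace, and the power statement in Section 7.1 has no allowance for any loss

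*Combined protocol and SAP*

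**What the plan says.** Enrolment (Section 3.2): "Ten subjects will be enrolled in this trial". Each patient is their own control (Section 3.1): "All participants will receive both treatments to be applied either at the proximal end or the distal end of the scar". Ten patients therefore give at most ten pairs.

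Power (Section 7.1): "There will be 80% power to detect an effect size of 1.3 standard deviations", "for the comparison of MED between any two treatment groups". The basis is given as follows: "This calculation is based a two-sided unpaired t-test with a type I error of 0.05". The section states no n, no attrition allowance, and no SD or correlation for the within-patient difference. MED is not defined and is not among the endpoints in Sections 3.4 and 3.5. Section 7.2 and the Study Summary plan a paired analysis.

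Replacement (Section 4.4.1): "A single subject withdrawn from the study will not be replaced". Then: "If two or more patients have withdrawn (with the exception of safety reasons) one of the subjects will be replaced with a new enrollee".

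Analysis set (Section 7.3): "This study will include only subjects who completed ALL study-related procedures and follow up".

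Month 3: Section 1.6.4 only encourages the final visit, and the Patient Treatment Schema in Section 3.1 allows a phone interview in place of it. The schedule in Section 6.11 puts photography and the VSS and POSAS questionnaires at that visit. The last ultrasound and the last biopsies are at Week 4.

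**The concern.** The three rules do not fit together. The power statement leaves no room for loss, the replacement rule does not make a loss good, and the analysis rule creates losses that are not withdrawals.

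The last of these matters most. After surgery there are seven scheduled contacts (three visits and four calls, Section 5.4). A patient can have complete ultrasound and biopsy data from both scar ends and still be excluded from every comparison because of one missed call, or because Month 3 was done by phone as the protocol allows. With at most ten pairs, each such exclusion is a tenth of the efficacy data. If the reason for incompleteness is related to how the scar heals or how the products are tolerated, the remaining pairs are also a selected group.

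**Working it through.** **1. Reproducing the plan's figure.** Inputs from Section 7.1: two-sided alpha 0.05, unpaired t-test, effect 1.3 SD. Input from Section 3.2: n = 10 per treatment. Power comes from the noncentral t distribution with df = 2n − 2 and noncentrality 1.3 × √(n/2).

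- n = 10: df 18, noncentrality 1.3 × √5 = 2.907, power 78.5%.
- n = 9: df 16, noncentrality 1.3 × √4.5 = 2.758, power 73.5%.
- n = 8: df 14, noncentrality 1.3 × √4 = 2.600, power 67.7%.

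The stated 80% is matched to within 2 points at 10 per group. The normal approximation gives 82.8% at 10 and 78.7% at 9. Section 7.1 does not say which formula was used.

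**2. Number analysed under Sections 4.4.1 and 7.3.**

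- One withdrawal, not replaced: 10 − 1 = 9.
- Two non-safety withdrawals, one replaced: 10 − 2 + 1 = 9.
- Three non-safety withdrawals, if the rule caps replacement at one (the wording is not explicit): 10 − 3 + 1 = 8.
- One patient who stays in the study but misses a call, or has Month 3 by phone: not a withdrawal, so no replacement. Section 7.3 leaves 9.

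**3. Power of the planned paired t-test.** Here df = n − 1 and the noncentrality is d × √n, where d is the effect in SDs of the within-patient difference. The documents do not say which SD the 1.3 refers to, so both readings are shown. If it is the SD of the difference, d = 1.3. If it is the between-site SD with within-patient correlation ρ, d = 1.3/√(2(1 − ρ)). The values of ρ are assumptions, because the documents give none.

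| Reading of 1.3 SD | d | 10 pairs | 9 pairs | 8 pairs |
|---|---|---|---|---|
| SD of the difference | 1.30 | 95.4% | 92.5% | 88.2% |
| Between-site SD, ρ = 0 | 0.92 | 73.5% | 67.7% | 60.9% |
| Between-site SD, ρ = 0.5 | 1.30 | 95.4% | 92.5% | 88.2% |

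On the between-site reading, 9 pairs reach 80% when ρ is about 0.26. Seven pairs still give 81.6% if d = 1.3.

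**4. Detectable effect for the paired test.** Solving for the d that gives 80% power: 0.996 at 10 pairs, 1.067 at 9 and 1.156 at 8. These values need no assumed effect or correlation, because they are expressed in SDs of the difference.

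**The case against.** The strongest reply is that the power loss is not established for the analysis that will be done. That stands. A reader might infer from Section 7.1 that all ten patients are needed for 80% power and that any single loss takes nine pairs to about 74% or lower. The documents do not support this. The 73.5% belongs to an unpaired test on 9 versus 9, whereas the plan analyses pairs. On the between-site reading, nine pairs fall to about 74% only if the correlation is about 0.14 or less, and Section 3.1 chose the within-patient design because it expects less variability. A reader might also infer that a lost pair costs the same under either test. That would require an effect of about 1.00 SD of the difference, which the documents do not state. With d = 1.3, going from 10 to 9 pairs costs about 3 points (95.4% to 92.5%).

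It can also be said that few patients will be lost. Section 6.10 gives visit and call windows, Section 4.4.1 requires at least three attempts before a patient is considered out, and Sections 4.4.1 and 8.5 generally keep patients with adverse events under follow-up. The documents give no dropout rate, so no expected number of completers is claimed here. The Month 3 phone option nevertheless shows that the protocol expects some incomplete patients.

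Finally, this is a ten-patient pilot whose primary aim is safety. That limits the weight of the power figures. It does not justify discarding measured pairs.

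**Conclusion.** The concern holds in a limited form. Section 7.3, read literally, removes patients with usable data from both scar ends, and Section 4.4.1 does not replace them. Section 7.1 makes no allowance for loss: on its own unpaired basis, power is 78.5%, 73.5% and 67.7% at 10, 9 and 8 per group.

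For the planned paired test the size of the loss cannot be determined. Nine pairs give 92.5% if 1.3 is in SDs of the difference. If 1.3 is in between-site SDs, they give 67.7% at correlation 0, 80% at about 0.26 and 92.5% at 0.5. No single power figure for nine pairs should be quoted until the SD of the within-patient difference, or the correlation, is stated.

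The conclusion rests on taking n = 10 from Section 3.2, since Section 7.1 gives none, and on a literal reading of Section 7.3. It applies to the secondary efficacy analysis. The Study Summary describes the primary safety analysis as descriptive.

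**What to change.** (a) Section 7.3: for efficacy, define the set for each paired TP-versus-base comparison as every randomised patient with both scar ends measured at that visit, regardless of other missed calls or visits. The cost is that N may differ slightly between visits, so each table should show its own N.

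(b) Section 7.1: restate the detectable effect for the paired test at the numbers the rules can deliver, namely 80% power for about 1.00, 1.07 and 1.16 SD of the within-patient difference at 10, 9 and 8 pairs. Say which endpoint is meant in place of MED, and give the SD of the difference or the correlation if one is available.

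While these sections are open, align the enrolment number in Section 3.2 with the replacement rule in Section 4.4.1, since a replacement would be an eleventh enrollee. This is close to clerical.

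All of this is protocol wording. Neither (a) nor (b) needs extra patients or procedures.

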##### **4.4.2 Data Collection and Follow-up for Withdrawn Subjects**

The sponsor of the study is responsible for following up on patients who develop adverse reactions to treatment. All study participants will undergo risk-appropriate follow-up until study-related adverse events have been fully treated and resolved.

[figure not shown]
### **5 Study Drug**

#### **5.1 Description**

Pentam 300 (pentamidine isethionate), an anti-protozoal agent, is a sterile, nonpyrogenic, lyophilized product. Pentamidine isethionate is a white crystalline powder soluble in water and glycerin, slightly soluble in alcohol and insoluble in ether, acetone, and chloroform. Currently used as an oral inhalation/intramuscular/intravenous antifungal agent.

Pentamidine isethionate, an aromatic diamidine, is known to have activity against *Pneumocystis carinii*. The mode of action of pentamidine is not fully understood. *In vitro* studies indicate that the drug interferes with protozoal nuclear metabolism by inhibition of DNA, RNA, phospholipid and protein synthesis.

It is chemically designated as 4,4-[1,5-pentanediylbis(oxy)]bis-benzenecarboximidamid with the following structural formula:

**C19H24N4O2•2C2H6O4S****592.68****Each vial contains:**

Pentamidine Isethionate . . . . . 300 mg

**Pharmacokinetics**

Biotransformation of pentamidine in humans is unknown. At least six metabolites have been identified in rats. Elimination of systemic drug is primarily renal, and half-life is increased in patients with renal dysfunction. Half-lives vary, depending on the route of administration. The terminal half-life is 2–4 weeks. Urinary excretion may persist for up to 8 weeks after discontinuation. Multiple dosing may result in drug accumulation, even in patients with normal renal function. No information on fecal excretion in humans is available.

Affected cytochrome P450 isoenzymes and drug transporters: CYP3A5, CYP2D6, CYP2C19, CYP1A1, CYP4A11. Previous data suggest that pentamidine was metabolized by the CYP2C19 isoenzyme; however, this has not been confirmed. In vitro data suggest that the CYP1A1, 3A5, and 4A11 isoenzymes may contribute to the metabolism of pentamidine, but data from healthy volunteers show that the CYP1A1 and 2D6 are the mediating enzymes in humans. Drug interactions with pentamidine are not well studied. Given these interactions, clinicians should be cautious using concurrent drugs that have similar toxicities.

**Preservative Free**

Sterile, Nonpyrogenic

Each vial contains: Pentamidine Isethionate 300 mg.

**Usual Dosage:** See Package Insert.

Reconstitute vial contents with Sterile Water for Injection or 5% Dextrose Injection only as directed in Package Insert.

Store dry product at 20° to 25°C (68° to 77°F) [see USP Controlled Room Temperature]. Protect dry product and reconstituted solution from light.

  
**APP**  
**APP Pharmaceuticals, LLC**  
 Schaumburg, IL 60173

NDC 63323-113-10 11310

**PENTAM® 300***(pentamidine isethionate  
for injection)***300 mg**

Lyophilized

**For IM or IV Use****Single-Dose Vial**

Rx only

401894D

LOT/EXP

  
 3 63323-113-10 0
**Base**

The vehicle used in this study is Pracasil™-Plus (PCCA #30-4655; PCCA PP). This non-aqueous silicone-based compounding agent contains the following ingredients:

- Cyclopentasiloxane
- Polysilicone-11
- PEG-16 Macadamia Glycerides
- Dimethicone
- C30-45 Alkyl Cetearyl Dimethicone Crosspolymer
- Pentaclethra Macroloba Seed Oil

- Oenocarpus Bataua Pulp Oil
- Phosphatidylcholine
- Tocopheryl Acetate
- BHT

## 5.2 Treatment Regimen

First dose will be applied 24 hours post-surgical scar excision, then scheduled every 48 hours. Approximately 1.8 mL (0.06 oz) of topical pentamidine (TP) or PCCA PP control will be topically applied via single dose containers provided the day of surgery and at their 2-week postoperative follow-up visit. Participants will receive two sets of single dose containers (set A and set B). One set will be randomized to contain TP with de-identified label; the other set will be randomized to contain PCCA PP with de-identified label. Each set (A and B) will contain 8 single dose containers, all with a de-identified label. The study drug will be applied every 48 hours. Specifically, topical agent (either TP or PCCA PP) will be applied to either the distal or the proximal end of the wound. Study participants will receive treatment application education during their pre-operative visit; further details provided in Section 6.1. Treatment duration is 4 weeks.

## 5.3 Preparation and Administration of Study Drug

Standard USP 40-NF 35, Chapter 795 compounding techniques will be followed. The compounding technician is responsible for compounding preparations of acceptable strength, quality, and purity and in accordance with the prescription or medication order. The compounding technician is also responsible for dispensing the finished preparation, with appropriate packaging and labeling, and in compliance with the requirements established by the applicable state agencies, state boards of pharmacy, federal law, and other regulatory agencies where appropriate.

Professional Compounding Centers of America Pracasil™-Plus (PCCA PP) is a topical silicone-based compounding base agent. Mayo Clinic Compounding Laboratory produced topical gel pentamidine (Pentam-300) in PCCA PP in USP (U.S. Pharmacopeial Convention)-grade facility. This gel will be sent to the Research Facility and stored at controlled room temperature (20-25°C) and stable until the end of the study period (4 weeks). Contact [name]., R.Ph. [contact] in the Research Pharmacy for more information.

Treatments will be provided in single dose containers for application every 48 hours following surgical recovery window (total 14 applications); total duration will be 4 weeks. Approximately 1.8 mL (0.06 oz) of pentamidine and within-patient placebo control will be topically applied to the designated scar region. Single dose containers will ensure each patient receives the same dosage.

## 5.4 Subject Compliance Monitoring

Subjects will be seen in the outpatient clinic as part of their follow-up (total of three follow-up visits in addition to four follow-up phone calls) during study duration. To ensure that study subjects are qualified in treatment application, each subject will complete an education session with the RN study coordinator. Subject compliance will be monitored during the follow-up visits and phone calls. Subjects will also receive a treatment log to record the date and time of treatment application as well as record any adverse events.

#### **5.4.1 Prior and Concomitant Therapy**

No topical therapies other than either TP or placebo PCCA PP are permitted for the duration of the study.

#### **5.5 Packaging**

The research pharmacy will order 300 mg Pentam vials via Rochester Methodist Campus (RMC) pharmacy purchasing specialists from APP Pharmaceuticals. Pentam vials will be stored within the research pharmacy (20-25°C) and sent to the compounding pharmacy when the study drug order is placed. The study drug order will be initiated by the study coordinator following patient consent, and as needed based on the date of surgery and 2 week postoperative visit. The Principle Investigator will sign the order which is then forwarded to the research pharmacy to be filled. For production, 300 mg Pentam (pentamidine isethionate) product will be compounded into non-aqueous silicone base vehicle (Pracasil™-Plus (PCCA #30-4655; PCCA PP) for 2% topical gel.

The compounding pharmacy will prepare the single containers for storage and dispensation by the research pharmacy. The research pharmacy will dispense a specified quantity of containers according to patient-specific prescription signed by IRB-authorized prescriber. The study coordinator will pick up the prescription from the research pharmacy and provide to the patient on visit 2 (day of surgery) and visit 3 (2 week postop clinic visit). Each dispensation will contain 8 active and 8 placebo containers to be applied every 48 hours; all containers (used and unused) will be returned by the patient at their next follow-up visits.

The research pharmacy will perform randomization schema to determine treatment to dispense for proximal versus distal scar areas. The research pharmacy maintains electronic records of investigational medication inventory and dispensation activities for the study; thus randomization will be performed for enrolled patients electronically via Medidata and Scientific Data Management System (SDMS). All Mayo Clinic Research Pharmacy staff members are required by policy to complete the Mayo Clinic Human Subject Protection and CITI Good Clinical Practice Training once every 3 years. The designated Research Pharmacy staff member assigned primary responsibilities for the study reviews all sponsor documents and prepares instruction sheets outlining storage, handling, electronic order entry and preparation of all investigational agents as indicated in the study protocol and pharmacy manual.

Following randomization, the distal location randomized treatment group (TP or PCCA PP) will be placed into a light-resistant bag with the below label on the exterior. Similar label will be provided for the proximal treatment group. Label will include caution statement: "Caution: New Drug--Limited by Federal (or United States) law to investigational use."

